Aim 1: To conduct a randomized, single-blinded, cross-over study testing the *insulin-only* bionic pancreas in a home-use setting in up to 30 adult subjects (≥ 18 years of age) with type 1 diabetes comparing two commercially available rapid acting insulin analogs, insulin lispro (Humalog, Lilly) and insulin aspart (Novolog, Novo Nordisk.) A final insulin-only bionic pancreas arm will use the experimental ultra-rapid insulin BC222 insulin lispro (BC Lispro, Adocia). The focus will be on determining which fast-acting insulin would be best for use in the iLet bionic pancreas system.

Up to 30 subjects will participate in three 7-day study arms using insulin lispro, insulin aspart, and BC222 lispro in the bionic pancreas in random order. The co-primary outcomes will be mean CGMG and fraction of time spent with CGMG <54 mg/dl with comparisons made between arms for individual participants. Secondary analyses will include time in glycemic ranges (<50 , <60 , <70 , $70-120$, $70-180$, >180 , >250 mg/dl), coefficient of variation, mean postprandial excursion (difference in CGMG from the time of meal announcement to the peak CGMG in the first 4 hours after the meal announcement) for both mixed meal challenges, number of symptomatic hypoglycemic events, grams of carbohydrate consumed to treat hypoglycemia, and TDD of insulin, between arms for individual subjects.

III. Subject Selection

III. a. Inclusion Criteria

1. Age ≥ 18 years and have had clinical type 1 diabetes for at least one year
2. Diabetes managed using an insulin pump for ≥ 6 months
3. Have used a CGM for at least one cumulative month over the last 12 months
4. Prescription medication regimen stable for > 1 month, including any adjunctive anti-diabetic medications (except for medications that will not affect the safety of the study and are not expected to affect any outcome of the study, in the judgment of the principal investigator)
5. Willing to remain within a 250-mile radius of MGH. No air travel will be allowed, and subjects will still be expected to follow the visit schedule as described.
6. Willing to wear one Dexcom CGM sensor, and one leur-lock compatible infusion set that must be replaced every other day
7. Have a mobile phone they will have access to at all times during the study for making contact with study staff

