No subjects will be excluded on the basis of gender or race. The requirement that subjects manage their diabetes using subcutaneous insulin infusion pump therapy is imposed because multiple daily injection therapy involves the use of long-acting basal insulin that would require an extended washout period.

III. b. Exclusion Criteria

1. Unable to provide informed consent (e.g. impaired cognition or judgment)
2. Unable to safely comply with study procedures and reporting requirements (e.g. impairment of vision or dexterity that prevents safe operation of the bionic pancreas, impaired memory, unable to speak and read English)
3. Current participation in another diabetes-related clinical trial that, in the judgment of the principal investigator, will compromise the results of this study or the safety of the subject
4. Pregnancy (positive urine HCG), breast feeding, plan to become pregnant in the immediate future, or sexually active without use of contraception
 - o Subjects must use acceptable contraception for the two weeks prior to the study, throughout the study and for the two weeks following the study.
 - o Acceptable contraception methods include:
 - Oral contraceptive pill (OCP)
 - Intrauterine Device (IUD, hormonal or copper)

- Male condoms
 - Female condoms
 - Diaphragm or cervical cap with spermicide
 - Contraceptive patch (such as OrthoEvra)
 - Contraceptive implant (such as Implanon, Nexplanon)
 - Vaginal ring (such as NuvaRing)
 - Progestin shot (such as Depo-Provera)
 - Male partner with a vasectomy proven to be effective by semen analysis
5. Current alcohol abuse (intake averaging > 3 drinks daily in last 30 days) or other substance abuse (use within the last 6 months of controlled substances other than marijuana without a prescription)
 6. Unwilling or unable or to avoid use of drugs that may dull the sensorium, reduce sensitivity to symptoms of hypoglycemia, or hinder decision making during the period of participation in the study (use of beta blockers will be allowed as long as the dose is stable and the subject does not meet the criteria for hypoglycemia unawareness while taking that stable dose, but use of benzodiazepines or narcotics or other central nervous system depressants, even if by prescription, may be excluded according to the judgment of the principal investigator)
 7. Renal failure requiring dialysis
 8. Estimated Glomerular filtration rate <15 mL/min/1.73²

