Ascensia Diabetes Care Contour Next One Glucose Meter: The Contour Next One glucometer is FDA approved and commercially available. Blood glucose measurements for Dexcom CGM calibrations and other required BG measurements will be obtained via finger stick with the Contour Next One in all study arms.

Precision Xtra Ketone Meter: The Precision Xtra ketone meter is FDA approved and commercially available. Blood ketone measurements will be obtained via fingerstick using the Precision Xtra ketone meter in all study arms.

V. d. Experimental Procedures and Data Collection

V. d. i. Screening Visit

- All subjects will have a screening visit to confirm eligibility.
- The subject will be interviewed, and the case report form will be completed by study staff to establish whether the subject is eligible to continue with the screening. Careful consideration will be given to ensure there are no medications or anything in their medical history that could affect their insulin absorption.
- A urine pregnancy test will be performed in pre-menopausal female volunteers. If the test is positive the volunteer will be informed of the result and the visit will be ended.
- Height, weight and blood pressure will be measured. An EKG will be performed in subjects who are either ≥50 years of age or who have had diabetes for ≥20 years.

- If the volunteer is not excluded based on historical criteria, blood pressure, EKG or urine pregnancy test, blood will be drawn for hemoglobin A1c, kidney function, anti-insulin antibody titers, and plasma, for future insulin antibody assays.
- Once all the laboratory results have been returned, a study MD or NP will review the case report form to determine subject eligibility. If subjects are not eligible to continue in the study the results of abnormal tests will be reported to the subjects and to a health care provider of their choosing.
- Subjects who have been screened and are eligible can participate without having to be re-screened for a period of 3 months. The study staff should verbally confirm that there have been no health events that would make them ineligible at every study visit and rescreen subjects for eligibility if it has been greater than three months.
 - Subjects who screen for the Test Run are not excluded from the RCT portion of the study and may participate if they meet the recruitment goals. They do not have to rescreen for the RCT portion if it will take place within 3 months of their Test Run screening.

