 - In the case of a low threshold alarm with no response from the participant and no success in locating them or their designated contact, the site principal investigator will be immediately informed. If remote monitoring shows ongoing hypoglycemia, a decision may be made to dispatch emergency medical services to the locations the participant is known to frequent.
 - Remote monitoring for hypoglycemia will be the same in all study arms.
- The remote monitoring system will generate an alarm if the CGM glucose is > 300 mg/dl for 90 minutes.
 - Participants will be reminded of the protocol for prolonged hyperglycemia, and the study provider will ensure they understand and will follow study procedures. Participants will be encouraged to follow up with any questions or concerns. All contact with the participants in response to hyperglycemia alarms will be documented.
 - Remote monitoring for hyperglycemia will be the same in all study arms.
- If there is a technical problem with the bionic pancreas that cannot be resolved over the phone, a member of study staff may be dispatched to the location of the subject to provide in-person assistance. The subject may be asked to come to the Diabetes Research Center or study staff may meet them in another public place. If this is not possible or would be too disruptive (i.e. in the middle of the night) the subject will be asked to take over their own glycemic control using their insulin pump until such time as a meeting can be arranged for in-person inspection of the device. This should occur in most cases within 12 hours. Staff will not go into subjects' houses or other non-public places; nor will they go to any place to meet the subject that is not public or where they do not feel safe.

V. d. v. Visit Procedures

Test Run Visit Procedures

Day 1:

- The body weight of the subject will be documented.
- A urine pregnancy test will be performed in female volunteers at the start of the Test Run. If the test is positive the volunteer will be informed of the result and the visit will be ended. The date of the last menstrual period will also be documented.
- Study staff will review any changes in the participant's medical history or medications to ensure continued eligibility, and any adverse events that may have occurred since their screening visit.

- The subjects will place a Dexcom G5 sensor and study staff will confirm they are doing it properly.

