- A urine pregnancy test will be performed in female volunteers at the start of the first arm. If the test is positive the volunteer will be informed of the result and the visit will be ended. The date of the last menstrual period will also be documented.
- Study staff will review any changes in the participant's medical history or medications to ensure continued eligibility, and any adverse events that may have occurred since their screening visit.
- The subjects will place a Dexcom G5 sensor and study staff will confirm they are doing it properly.
- Study staff will provide supplies and review the study procedures. The insulin the subject has been assigned to for that week will be provided. Study staff will supervise the setup of the iLet and infusion set.
- The control algorithm will be initialized only with the subject's weight. Diagnostics will be performed to ensure that the Dexcom CGM device is appropriately calibrated and that all the components of the bionic pancreas are in good communication with each other.
- The subject's own insulin infusion pump will be stopped and disconnected, and its infusion set will be removed.

removed.

- Study staff will start the bionic pancreas and will verify that data streaming is working prior to the subject leaving the Diabetes Research Center.

Days 1-7:

- The subjects will calibrate the Dexcom CGM twice daily, preferably before breakfast and supper, using the Contour Next One.
 - Subjects will be advised to delay calibration if there is a steep rise or fall in the blood glucose (>2 mg/dl/min) or if there has been carbohydrate intake in the last 30 minutes. In the immediate aftermath of carbohydrate intake, it is possible for the BG to be rising without a change in interstitial fluid glucose. If a calibration is delayed for any of these reasons, it will be performed at the next opportunity.

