- All study devices, including the iLet BP and the study glucometer will be downloaded. The memory of the BP will be wiped and it will be re-initialized for the next study period. Diagnostics will be performed to ensure that the Dexcom CGM device is appropriately calibrated and that all of the components of the bionic pancreas are in good communication with each other.
- Used and unused insulin vials will be returned to prevent the subject from using the wrong insulin during the wrong week.
- Anti-insulin antibody and plasma blood samples will be collected.
- Subjects will have the option to begin the next arm of the study on the same day they complete the previous study arm.
 - If subject choose this option, they will start over with Day 1 procedures:
 - If the Dexcom CGM has not already been replaced, it will be replaced at this time.
 - Study staff will provide supplies, including the next week's insulin, and review the study procedures.
 - Study staff will supervise the setup of the iLet and infusion set. Participants will need to fill the iLet with a new reservoir and place a new infusion set at the start of each new study arm.
 - Study staff will start the bionic pancreas and will verify that data streaming is working prior to the subject leaving the Diabetes Research Center.
 - If subjects choose to not continue directly to the next arm of the study, the Dexcom CGM sensor will be removed, all bionic pancreas infusion sites will be removed, subjects will put their own pump back on, and they will be discharged.
 - A provider (MD or NP) will review the last several hours of insulin dosing and assist the subject in resuming their usual care.
 - The next arm of the study will be scheduled to begin up to 14 days from the end of the previous study arm.

Final Day 7 Visit:

- At the end of the 7-day period, subjects will return to the clinic and answer the post questionnaires for the study arm.

- The body weight of the subject will be documented
- Any changes to medications or medical history and any adverse events that may have occurred since the last study visit will be documented
- Anti-insulin antibody and plasma blood samples will be collected
- The Dexcom CGM sensor and all bionic pancreas infusion sites will be removed.
- All study devices, including the iLet BP and the study glucometer will be downloaded.
- Used and unused insulin vials will be returned.

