- Subjects experience one episode of diabetic ketoacidosis (DKA) requiring hospitalization
 - Hyperglycemic events will be classified as DKA if the following are present:
 - Symptoms including but not limited to polyuria, polydipsia, nausea or vomiting
 - Serum ketones $> 1.5 \text{ mmol/L}$ or large/moderate urine ketones
 - Either arterial blood pH < 7.30 or venous pH < 7.24 , or serum bicarbonate < 15
 - Treatment provided in a healthcare facility
- Subjects experience one episode of severe hypoglycemia, defined as requiring the assistance of another person due to altered consciousness, and required another person to actively administer carbohydrate, glucagon or other resuscitative actions. This means the participant was impaired cognitively to the point that he/she was unable to treat himself/herself, was unable to verbalize his/her needs, was incoherent, disoriented, and/or combative, or experienced seizure or coma. If plasma glucose measurements are not available during such an event, neurological recovery attributable to the restoration of plasma glucose to normal is sufficient evidence that the event was induced by a low plasma glucose concentration.
- The investigator believes it is unsafe for the participant to continue in the study
- A participant becomes pregnant

- The participant requests that the study be stopped

If more than 1 subject must be withdrawn from the study for DKA requiring hospitalization or seizure or unconsciousness associated with hypoglycemia the study will stop and a vote of the DSMB will be required to restart it. All serious and unexpected events will be reported to the DSMB within 72 hours.

Note that subjects may discontinue participation at any time and subjects may be removed from the trial for other reasons, for instance failure to comply with study procedures or concurrent illness that is unrelated to the bionic pancreas but that precludes safe participation. Discontinuation of participation for these reasons will not contribute to a decision to discontinue the trial.

IX. c. Adverse Event Definitions and Reporting Guidelines

Definitions

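### The RCT schedules a pregnancy test only before the first arm, so whether the unapproved BC222 lispro is started on a same-day test depends on arm order

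*Combined protocol and SAP*

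**What the plan says.** **The criterion.** Section III.b, exclusion 4, reads "Pregnancy (positive urine HCG), breast feeding, plan to become pregnant in the immediate future, or sexually active without use of contraception". The criterion is tied to a urine test. Contraception is required from two weeks before the study until two weeks after it. Section IX.b lists "A participant becomes pregnant" among the reasons for ending an individual's participation.

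**When the test is done.**
- Screening (V.d.i): "A urine pregnancy test will be performed in pre-menopausal female volunteers".
- Test Run, Day 1 (V.d.v): "A urine pregnancy test will be performed in female volunteers at the start of the Test Run". BC222 lispro is supplied and started at that same visit.
- RCT, Day 1 Visits (V.d.v): "A urine pregnancy test will be performed in female volunteers at the start of the first arm". If the result is positive, the volunteer is told and the visit ends.

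**What happens between arms.** The Day 7/Day 1 list in V.d.v covers questionnaires, body weight, a review of history and medication to confirm continued eligibility, device downloads, return of insulin, and blood samples for antibodies. It lists no urine HCG. Those who go straight on repeat the Day 1 procedures, but the Day 1 test is itself confined to the first arm.

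**Timing.** Aim 1 (section II) states: "Up to 30 subjects will participate in three 7-day study arms using insulin lispro, insulin aspart, and BC222 lispro in the bionic pancreas in random" (that is, the sequence of arms is randomized). On the shortest gap: "Subjects will have the option to begin the next arm of the study on the same day they complete the previous study arm". On the longest: "The next arm of the study will be scheduled to begin up to 14 days from the end of the previous study arm". Section V.b states that BC222 lispro has no FDA approval and has not previously been used in a bionic pancreas.

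**The concern.** The plan treats pregnancy as a reason not to enter and a reason not to continue, and it names the test that decides the matter. It also re-checks eligibility at each change of arm. Yet that re-check leaves out the deciding test, so two of the three arms begin without it.

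The plan is also uneven in how it handles the same product. In the Test Run, with daytime supervision and three days of use, every woman is tested on the day she starts BC222 lispro. In the RCT, with seven days of use at home, she is tested that day only if randomization puts BC222 lispro first. No reason is given for the difference.

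At stake is participant safety and the reliability of the discontinuation rule in IX.b, which can be applied only if a pregnancy is recognized. The endpoints and their analysis are not affected.

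**Working it through.** The plan states no interval from test to first dose, so there is no figure of its own to reproduce. The check is calendar arithmetic.

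**Inputs**
- Arm length L = 7 days, three arms, random order (Aim 1).
- Gap between arms g = 0 to 14 days (V.d.v, Day 7/Day 1 Visits).
- Last scheduled RCT test on day 0, the start of arm 1 (V.d.v, Day 1 Visits).

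**Formulas**
- Start of arm 2 = L + g
- Start of arm 3 = 2 × (L + g)
- End of arm 3 = 2 × (L + g) + L

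**Results (days since the last test)**

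| | g = 0 | g = 14 |
|---|---|---|
| Arm 1 starts | 0 | 0 |
| Arm 2 starts | 7 | 7 + 14 = 21 |
| Arm 3 starts | 2 × 7 = 14 | 2 × 21 = 42 |
| Arm 3 ends | 14 + 7 = 21 | 42 + 7 = 49 |

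If Day 1 to Day 7 is counted as six elapsed days, arm 2 starts at 6 to 20 days and arm 3 at 12 to 40 days. The protocol places the visit at the end of the 7-day period, which favors the figures in the table.

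**How often BC222 lispro is not first.** Three treatments have 6 possible orders. BC222 lispro is second in 2 and third in 2, so 4/6 = two thirds of orders place it after the only RCT test. Applying that share to participants assumes equal placement across periods. Section V.d.ii refers to three visit orders without listing them, so the actual share cannot be confirmed.

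**Does the three-month rescreening rule (V.d.i) close the gap?** Rescreening would bring a new test, but only once three months have passed since screening. Taking three months as 90 to 92 days, arm 3 at its latest (day 42) still falls inside the window if arm 1 began within 90 − 42 = 48 to 92 − 42 = 50 days of screening. With back-to-back arms the limit is 90 − 14 = 76 to 92 − 14 = 78 days. So the rule may trigger a test for late starters, but it need not.

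**Effect of testing at each arm start.** The interval from test to start of any study insulin becomes 0 days, and no test is more than 7 days old during an arm.

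**The case against.** The strongest reply is that the plan already controls pregnancy risk by other means:
- Exclusion 4 bars women who plan a pregnancy or are sexually active without contraception, and acceptable contraception must continue throughout the study.
- V.d.i asks staff to confirm verbally at every visit that nothing has made the participant ineligible.
- The Day 7/Day 1 visit reviews medical history and medication.
- VI.a.2 lists the date of the last menstrual period among the data for all arms.

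This largely stands. It would be wrong to infer that later arms start with no check, or that detection rests wholly on the participant volunteering the information. But none of these safeguards is a pregnancy test. The Day 7/Day 1 list does not mention menstrual dating, and nothing says that a late period leads to a test.

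Some stronger readings are also not supported:
- *That the first-arm test is out of date by the later arms.* The plan sets no expiry for the HCG. The only validity period it states is three months for screening, and 42 days lies within that.
- *That 42 days is typical.* It requires both gaps at their limit. With no gaps, arm 3 starts at 14 days.
- *That BC222 lispro carries a known risk in pregnancy.* V.b reports more than 280 people exposed, with no risks identified beyond those of insulin products. That does not establish safety in pregnancy, but it gives no evidence of a particular harm.
- *That the plan contradicts itself.* An entry exclusion, a discontinuation rule and a baseline test can coexist, and the restriction to the first arm is explicit.

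**Conclusion.** The gap is real and modest. In the RCT, arm 2 starts 7 to 21 days and arm 3 starts 14 to 42 days after the last scheduled pregnancy test. Arm order therefore decides whether BC222 lispro is started on a same-day test, whereas the Test Run always provides one.

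The intervals rest on 7-day arms and the stated 0 to 14 day gaps. The two-thirds share rests on the assumption that BC222 lispro is placed equally often in each period. The documents do not say how many participants could become pregnant, and they give no pregnancy rate, so no expected number of undetected pregnancies can be calculated. With contraception required throughout, that number may well be small.

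This is a cheap improvement of low to moderate severity. It concerns how eligibility is verified in the RCT. It does not apply to the Test Run and does not bear on the statistical results.

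**What to change.** Reconcile the RCT Day 1 and Day 7/Day 1 lists in V.d.v with exclusion 4 (III.b), the Test Run Day 1 list and the discontinuation rule (IX.b), so that the eligibility re-check at the start of each arm includes the urine HCG that defines the criterion. A positive result would be handled by the provision already in the RCT Day 1 list; no new clinical rule is needed.

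At the same time, reconcile who is tested. The Test Run and RCT Day 1 lists say female volunteers, whereas V.a, V.d.i and VI.a.1 say pre-menopausal women.

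**Cost.** At most two extra urine tests per woman, or 2 × 30 = 60 in total even if all 30 RCT participants were tested. Participants already attend to start each arm, so no visit is added. The downside is a few minutes per visit and two short edits to the protocol.
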